6.1.3 Post-Treatment Period

After discontinuation of treatment with ISIS 420915, patients will enter the 3-month post-treatment evaluation period. This period consists of clinic and non-clinic visits for safety monitoring as outlined in the Schedule of Procedures (Appendix A and C). Weekly platelet and every 2-3 week serum creatinine testing is required for a minimum of 6 weeks after the last dose of Study Drug (this includes early termination patients as well as patients that complete the full treatment period). Patients that terminate treatment early and do not withdraw consent should have the post-treatment visit Week 169 conducted 3 months after the last dose of Study Drug. The 3-month post-treatment evaluation period may be omitted if the patient discontinues treatment in this study, but is continuing to receive treatment with ISIS 420915 via another mechanism.

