8.5.4 Safety Monitoring Rules for Platelet Count Results

Platelets will be monitored weekly throughout the treatment period and for a minimum of 6 weeks after the last dose of Study Drug (this includes early termination patients as well as patients that complete the full treatment period). For patients participating in the Post-Treatment Evaluation Period, frequency of testing after 6 weeks from the last dose of Study Drug will be determined by the Investigator in consultation with the Study Medical Monitor.

All platelet count results must be promptly reviewed by the Investigator to ensure that the count has not met the stopping rule

If for any reason there is more than 14 days between platelet values (e.g. lab report of an unreadable sample due to clumping, hemolysis, or quantity not sufficient, or a missed lab assessment), the Investigator will contact the patient to hold dosing until a new platelet value is obtained and reviewed.

If a patient's platelet counts fall below 100,000/mm³, additional lab tests may be requested as determined by the Investigator in consultation with the Study Medical Monitor.

Due to the 3 to 5-year study duration it is anticipated that patients may undertake travel including vacations, which may impede weekly platelet monitoring. In some situations it may be possible to arrange for local laboratory testing or use of the home healthcare service at their temporary location. The intent is to maintain weekly platelet monitoring and dosing where possible, as well as Investigator site contact with the study patients. However, if the above options are not possible, a temporary interruption of study treatment will be planned with a prompt blood draw upon the patient's return which must be reported and reviewed by the Investigator prior to the patient resuming dosing.

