8.9 Withdrawal of Patients from the Study

Patients must be withdrawn from the study for any of the following:

- Withdrawal of consent
- The patient is unwilling or unable to comply with the protocol
- The patient receives a liver transplant

Other reasons for withdrawal of patients from the study might include:

- At the discretion of the Investigator or Sponsor for medical reasons
- At the discretion of the Investigator or Sponsor for noncompliance
- Significant protocol deviation
- Administrative decision by the Investigator or Sponsor
- ISIS 420915 becomes commercially available in the local country (patients in Year 4 or Year 5)
- ISIS 420915 is rejected by the regulatory authority in the local country

All efforts will be made to complete and report the observations as thoroughly as possible up to the date of withdrawal. All information, including the reason for withdrawal from Study, must be recorded in the eCRF.

Any patient who withdraws consent to participate in the study will be removed from further treatment and study observation immediately upon the date of request. Patients withdrawn for any reason should be encouraged to complete the ET visit at the time of withdrawal (Appendix A).

Patients who receive a liver transplant should be encouraged to return to the clinic to complete the ET visit as soon as feasible after the transplant procedures.

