10.2 Sample Size Considerations

No sample size calculations were performed as this is an extension study to the double-blind, placebo-controlled ISIS 420915-CS2 study. Approximately 135 patients are planned in the ISIS 420915-CS2 study and may be eligible to enroll into this study.

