The mNIS+7 assessment is conducted at Weeks 26, 52, 78, 104, 130, and 156. Norfolk QOL-DN questionnaire is conducted at Weeks 26, 52, 78, 104, 130, 156, Y4-W52, and Y5-W52. The Norfolk QOL-DN questionnaire should be the first assessment performed at these visits. If ISIS 420915 administration, ERG, or ophthalmology examinations are to be performed on the same day as an mNIS+7 assessment, they should be performed after the mNIS+7 assessment is complete. For the Week 78 and 156 visits, two mNIS+7 assessments will be performed on separate days. A maximum of 2 weeks from the visit (Week 78 or Week 156) will be allowed to complete both assessments.

For Weeks 4-52 there is a \pm 7-day visit window. For Years 2-3 the visit window is \pm 10-day. After Year 3 the visit window is \pm 14-day. All reasonable attempts should be made to ensure compliance with the visit schedule as outlined in the schedule of procedures (the protocol Appendix A). However, if a

visit does not occur or is delayed, all subsequent visits should be calculated based on the time elapsed since Day 1 rather than from the date of the previous visit.

After completion of the treatment period, patients will enter the 3-month post-treatment evaluation period. This period consists of clinic and non-clinic visits for safety monitoring as outlined in the schedule of procedures (the protocol Appendix A and C). Weekly platelet and every 2-3 week serum creatinine testing are required for a minimum of 6 weeks after the last dose of Study Drug (this includes early termination patients as well as patients that complete the full treatment period). Patients that terminate treatment early and do not withdraw consent should have the post-treatment visit conducted 13 weeks after the last dose of Study Drug.

Patients may be allowed to take Vyndaqel® after 18 months at the discretion of the Study Medical Monitor.

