- o For both studies the post-treatment period starts on the day after the treatment period and ends on the day of the patient's last contact date within the study.

• For safety endpoints except for ERG:

- The on-treatment period for the parent study spans the time during which the study treatment is administered from the CS2 Study Day 1 until 7 days after the last dose of medication in the parent study. The on-treatment period for the OLE study is from the CS3 Study Day 1 until 7 days after the last dose of medication in the OLE study.
- For both studies the safety post-treatment period starts on the day after the safety treatment period and ends on the day of the patient's last contact date within the study.
- For both studies the Safety on-study period spans the time drug is first administered until the day of the patient's last contact date within the study.
- The period for the longitudinal safety analysis spans the time from the first dose of ISIS
 420915 in the parent study and ends on the day of the patient's last contact date within the study. The subject's last contact date is defined as follows:
 - (1) for subjects who signed an informed consent form in the OLE study, it is the last contact date within the OLE study;
 - (2) for subjects who did not sign an informed consent form in the OLE study but had been administered ISIS 420915 in the parent study, it is the last contact date within the parent study. The details of longitudinal safety analysis for AEs and safety lab results will be addressed in section 3.3.

For ERG:

The on-treatment period for the parent study spans the time during which the study treatment is administered from the CS2 Study Day 1 until 28 days after the last dose of medication in the parent study. The on-treatment period for the OLE study is from the CS3 Study Day 1 until 28 days after the last dose of medication in the OLE study.

- For both studies the safety post-treatment period starts on the day after the safety treatment period and ends on the day of the patient's last contact date within the study.
- The PK on-study period for the OLE study spans the time ISIS420915 is administered in the OLE study (CS3 Study Day 1) until the day of the patient's last contact date within the OLE study.

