- Visit based safety assessments (scheduled and unscheduled) will be assigned to a visit according to analysis visit windows in the table 3 of Appendix 3 Analysis Visit Windows, even if they occurred within one of the visit windows. Except for platelet assessments from the local laboratory, local laboratory assessment will not be assigned to a visit and the nominal visit only will be presented in the listings. Safety assessments that occurred during the safety post-treatment period (i.e., more than 7 days after the last dose of study drug) will not be included in

the visit based safety analyses during the safety treatment period. If there are multiple visits within a window, the visit nearest the target day will be used unless two visits are equally near, in which case the average will be used. Note that safety assessments that are not utilized in the visit based summary tables will appear in listings and be used in the determination of treatment-emergent shifts or abnormalities.

• To assess the impact of treatment discontinuation on safety parameters, data from visit based safety assessment in the post treatment phase may also be summarized with respect to the elapsed time from last dose. Assessment will be slotted into follow-up visit windows according to elapsed time from last dose based on the scheduled assessments during the post-treatment evaluation period of the study. The planned windows for this investigation are shown in the table 4 of Appendix 3 Analysis Visit Windows.

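### The SAP does not close the post-treatment period when a patient continues ISIS 420915 outside the study, so tables meant to describe stopping treatment can include on-drug values

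*Combined protocol and SAP*

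**What the plan says.** **Leaving the study while staying on drug.** Protocol 3.1 foresees patients who stop treatment in CS3 and continue ISIS 420915 by another route, including early access after Year 5. Protocol 8.9 lists local commercial availability as a possible reason for withdrawal in Years 4 and 5. On follow-up for those who continue, Protocol 6.1.3 says: "The 3-month post-treatment evaluation period may be omitted if the patient discontinues treatment in this study, but is continuing to receive treatment". This is permission, not a requirement.

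**Testing after the last dose.** Protocol 8.5.4 requires weekly platelet counts "for a minimum of 6 weeks after the last dose of Study Drug (this includes early termination patients as well as patients" who complete treatment. Protocol 6.1.3 and Appendix A (note 13) add serum creatinine every 2-3 weeks.

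**Period definitions in the SAP.** SAP 2.1 states "After completion of the treatment period, patients will enter the 3-month post-treatment evaluation period" and does not carry over the omission clause. In SAP 3.2.1.1.4 the safety on-treatment period runs "until 7 days after the last dose of medication in the OLE study"; for TTR, RBP4, BMI and mBMI the allowance is 28 days. The safety post-treatment period then "starts on the day after the safety treatment period and ends on the day of the patient's last contact date within the study". SAP 3.2.1.4 repeats these cut-offs and lists post-treatment summary tables among the outputs. SAP 9.2.2.2, for combined CS2 and CS3 data, counts from the last dose of ISIS 420915 and does not mention outside supply.

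**Purpose.** SAP 3.2.1.3 ties the post-treatment safety summary to treatment discontinuation: "To assess the impact of treatment discontinuation on safety parameters, data from visit based safety assessment in the post treatment phase may also be summarized".

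**The concern.** A patient who moves from study supply to another supply has not stopped the drug. The SAP nevertheless counts from the last study dose and treats later in-study assessments as post-treatment. No exclusion, flag or separate stratum for continued dosing appears in SAP 3.2.1.1.4, 3.2.1.3, 3.2.1.4, 9.2.2.2 or Appendix 3.

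At stake is what the off-drug tables mean. Platelet and renal safety are central to the primary objective, and thrombocytopenia and renal impairment are both adverse events of special interest (SAP 3.3.2.1). If on-drug values are mixed in, the summaries move toward the treated level, and any recovery after stopping would look slower or smaller than it is.

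**Working it through.** There is no planned figure to reproduce. Protocol 10.2 says "No sample size calculations were performed as this is an extension study", and the point concerns how assessments are classified. The check therefore traces the rules.

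**Step 1. Inputs.** Cut-offs: last OLE dose + 7 days (safety) and + 28 days (PD), from SAP 3.2.1.1.4 and 3.2.1.4. Follow-up windows: SAP Appendix 3, Tables 2 and 4. Assumption: weekly dosing from the outside supply starts 7 days after the last OLE dose.

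**Step 2. Classify a still-dosed patient's samples.**

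| Days after last OLE dose | Safety period | Platelet window | Creatinine window | TTR/RBP4 |
|---|---|---|---|---|
| 14 | post-treatment | Week 2 (10-16) | Week 2 (8-20) | still on-treatment |
| 28 | post-treatment | Week 4 (24-30) | Week 4 (21-34) | still on-treatment |
| 42 | post-treatment | Week 6 (38-65) | Week 6 (35-65) | post-treatment, no window |
| 91 | post-treatment | Week 13 (66-121) | Week 13 (66-121) | Week 13 (61-121) |

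By day 91 this patient has had 91/7 = 13 outside doses, or 12 if the sample precedes that day's dose, and every value is labelled post-treatment.

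**Step 3. Which measures are exposed.** Only platelets and serum creatinine have windows before Week 13, and these are the tests required for at least six weeks after the last dose. The other measures in Tables 2 and 4 have a single window, days 61-121, so they are exposed only if the Week 13 visit takes place. The early termination visit is ideally within 14 days of the last dose (Appendix A, note 14), so its PD sample stays on-treatment.

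**Step 4. Contrast with a patient truly off drug.** Using the nonclinical plasma half-life of 17.0 days (Protocol 2.3.3), the fraction remaining is 0.5^(42/17) = 0.18 at day 42 and 0.5^(91/17) = 0.024 at day 91. By the later windows the two kinds of patient differ substantially in exposure.

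**Step 5. Illustration only.** Let p be the share of Week 13 TTR values from still-dosed patients and r the true off-drug change. The table mean is p × (-75%) + (1 - p) × r. The -75% is the 300 mg result in healthy volunteers (Protocol 2.3.4); p and r are assumptions.

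| p | r = 0% | r = -20% |
|---|---|---|
| 0 | 0% | -20% |
| 0.10 | -7.5% | -25.5% |
| 0.25 | -18.8% | -33.8% |
| 0.50 | -37.5% | -47.5% |

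For example, 0.25 × (-75) + 0.75 × (-20) = -18.75 - 15 = -33.75. The documents give no comparable on-drug and off-drug figures for platelets or creatinine.

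**The case against.** The strongest reply is that the plan already limits the problem.

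- **Withdrawal.** SAP 3.2.1.3 reports data up to the point of withdrawal for patients who withdraw from the OLE study. Withdrawal for commercial availability (Protocol 8.9) falls under that rule. This stands. It does not clearly cover a patient who completes or stops treatment without withdrawing, and Protocol 8.8 treats stopping treatment and leaving the study as separate events.
- **Follow-up can be skipped.** The omission clause exists for these very patients, and those who skip follow-up contribute little or nothing. This stands, but omission is optional.
- **The six-week testing may lapse too.** In Protocol 6.1.3 the testing rule and the omission clause share one paragraph, so omission may cover the testing. Protocol 8.5.4 states the six-week minimum before it turns to patients participating in the post-treatment period, which suggests the opposite. The text does not settle this.
- **Optional, descriptive tables.** The safety summary is worded as optional and there are no formal hypotheses (SAP 1.3). No error rate is affected. However, SAP 3.2.1.4 lists the tables as outputs.
- **Combined data.** The last dose in SAP 9.2.2.2 could be read to include outside doses. The exposure definition in SAP 3.2.1.1.5 points the other way, since it takes the last dose given in the OLE study. SAP 9.2.2 also refers to a separate ISS SAP that is not available here.

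A reader might infer that every value taken after transfer enters the Week 2 to 13 tables. The documents do not support that. Most measures have only the Week 13 window, local laboratory values other than platelets are not assigned to a visit, and the period ends at the last contact within the study.

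**Conclusion.** The concern holds in a limited form. As written, the SAP can place on-drug values in tables intended to describe stopping treatment. This affects patients who finish or stop CS3 treatment, continue ISIS 420915 elsewhere and still have follow-up samples. Platelets and serum creatinine at Follow-up Weeks 2 to 6 are the most exposed, then any Week 13 visit.

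The size is unknown. It is tempting to infer that the group is large because continuing elsewhere is a planned route. The documents do not give the number who transfer, and the relevant group is only those who transfer and still have in-study samples. The TTR figures above show direction under assumed inputs and are not estimates. Nor do the documents support a claim that combined CS2/CS3 tables of TTR after stopping are distorted: SAP 9.2.2.3 lists TTR and RBP4 as on-treatment only, and the discontinuation purpose is stated for safety parameters, not for PD.

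The change is still worth making because the tables have a stated purpose that the period definition does not secure.

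**What to change.** 1. In SAP 3.2.1.1.4 and 3.2.1.4, and in 9.2.2.2 for the combined post-treatment outputs, end the post-treatment period at the first dose of ISIS 420915 received outside the study. Exclude later values from post-treatment summaries and list them with a flag.
2. Name the source of that date: an explicit record that outside ISIS 420915 was started, and when. The concomitant-medication record may not hold it. Protocol 8.10.1 restricts concomitant therapy to drugs the protocol does not specify, and SAP 3.2.3 restricts it to medication taken while investigational product is being taken in this study.
3. State a fallback. If the date is missing, patients recorded as continuing by another mechanism are either excluded from the post-treatment summaries or shown separately.
4. Reconcile Protocol 6.1.3 and 8.5.4 on whether the six-week platelet and creatinine testing applies when the post-treatment period is omitted. Which rule should apply is for the sponsor to decide.

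The cost is SAP wording, one derived date, confirmation (or collection) of the outside start date, and slightly fewer patients in the post-treatment tables.

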3.2.1.4 Data Summary Plan

The table below details what data will be included in the summary and analysis output by endpoint type. Data summarized or analyzed at each interim analysis will be based on data collected up to the data cut date. It is possible that on-treatment data and post-treatment data available for each interim analysis is different from the final analysis at the end of study because data collected after each interim analysis data cut may slot into different treatment period. Outputs will be updated for each interim analysis and for the final analysis. In select instances the data for a type of endpoint that is summarized or analyzed may not be consistent with the rules in the table below; such exceptions will be noted in this document.

Endpoint type	Output type	Comment/definition
Efficacy	-Listings -On-treatment (CS2&CS3) summary/analysis tables -Post-treatment summary tables	-On-treatment (CS2 period):The CS2 Study Day 1 S Date of assessment S Last dose date in parent study+ 52 days -On-treatment (CS3 period): CS3 STUDY DAY 1 \$ Date of assessment S Last dose date of OLE study+ 52 days -showing both CS2 visits and CS3 visits. Note the results of the analyses at the CS2 visits will not be the same as the results from the CS2 study as this table only includes patients in the CS3 FASPost-treatment: Date of assessment > last dose date of OLE study + 52 days -Visit defined by analysis visit window
PD, BMIand mBMI	-Listings -On-treatment (CS2&CS3) summary/analysis tables -Post-treatment summary tables	-On-treatment (CS2 period): The CS2 Study Day 1 S Date of assessment S Last dose date in parent study+ 28days -On-treatment (CS3 period): CS3 STUDY DAY 1 S Date of assessment S Last dose date of OLE study+ 28days -showing both CS2 visits and CS3 visits. Note the results of the analyses at the CS2 visits will not be the same as the results from the CS2 study as this table only includes patients in the CS3 FAS.

Endpoint type	Output type	Comment/definition
		-Post-treatment: Date of assessment> last dose date+ 28days -Visit defined by analysis visit window
Safety Endpoints: ECG, Lab, vitals sign (including body weight)	-Listings -On-treatment summary tables (CS3) -Post-treatment summary tables	-On-treatment (CS3 period): CS3 Study Day Is Date of assessment 5 Last dose date + 7 days -Post-treatment: Date of assessment> last dose date+ 7 days -Visit defined by analysis visit window
Safety Endpoints: ERG and ophthalmology examinations	-Listings -On-treatment summary tables (CS3) -Post-treatment summary tables	-On-treatment (CS3 period): CS3 Study Day ls Date of assessment 5 Last dose date+ 28 days -Post-treatment: Date of assessment> last dose date+ 28 days -Visit defined by analysis visit window
Safety Endpoints: abnormal lab, worst ECG, meeting Stopping rule	-Listings -On-study summary tables (CS3)	-Abnormal lab analyses described in Sections 3.3.4.1 to 3.3.4.3 include post-baseline data collected from CS3 Study Day 1 up to the day of the patient's last contact date within the study
Safety Endpoints: AE	-Listings -On-treatment (CS3) summary tables -On-study (CS3) summary tables	-On-treatment: CS3 Study Day ls Date of assessment 5 Last dose date + 7 days -On-study summary tables includes all treatment emergent adverse event (TEAE) in the OLE study, including those with onset dates> last dose date + 7 days
Selected Safety Endpoints: abnormal lab and AEs	- Longitudinal safety summary for overall parent study and OLEstudy	- Longitudinal safety summary for overall parent study and OLE study include data collected from the first dose of ISIS 420915 in the parent study and ends on the day of the patient's last contact date within the study, (1) for subjects who enrolled in the OLE study, it is the last contact date within the OLE study; (2) for subjects who are not enrolled in the OLE study but had been administered ISIS 420915 in the parent study, it is the last contact date within the parent study.
Concomitant medications	-Listings -On-treatment (CS3) summary tables -On-study (CS3) summary table	-On-treatment: CS3 Study Day ls Date of assessment s Last dose date + 7 days -On-study summary tables includes all concomitant medication in the OLE study, including those with onset dates > last dose date+ 7 days
Immunogenicity	-Listings -On-study (CS2 and CS3)	-On-study summary/analysis tables include data collected from the CS2 Study Day 1 up to the day of the

Endpoint type	Output type	Comment/definition
	summary/ analysis tables	patient's last contact date within the study (showing both CS2 visits and CS3 visits) -Visit defined by analysis visit window.
PK	-Listings -On-study (CS3) summary/ analysis tables	-Summary/analysis tablesinclude data collected from CS3 Study Day 1 up to the day of the patient's last contact date within the study -PK concentration will be summarized based onnominal scheduled visits (showing CS3 visits)

